**Table 3-2 Study drug dose levels for sacubitril/valsartan**

age groups 1 and 2 *	
Dose levels for pediatric formulation	
Dose level 1	0.8 mg/kg bid.
Dose level 2	1.6 mg/kg bid.
Dose level 3	2.3 mg/kg bid.
Dose level 4	3.1 mg/kg bid.
Dose levels for adult formulation	
Dose level 1	50 mg bid.
Dose level 2	100 mg bid.
Dose level 3	150 mg bid.
Dose level 4	200 mg bid.

\*Note: sacubitril/valsartan target dose (dose level 4) for age groups 1 and 2 is 3.1 mg/kg bid. (see [Section 4.2](#) for additional details).

If a subject is unable to tolerate up-titration to a higher sacubitril/valsartan dose level or at the discretion of the investigator, subjects may be maintained on lower dose levels of sacubitril/valsartan (dose level 1-3, see [Table 3-2](#)). In case of a consecutive 3-month interruption of study treatment, subject should be discontinued from the study and should complete Visit 599.

An outline of the study design is presented in [Figure 3-1](#). Depending on when and where the patient is enrolled, the duration of the study varies from 1 to approximately 4.5 years.

The OLE study drug starting dose will depend either upon the dose of ACEI/ARB that the subject was transitioned to after completion of the PANORAMA-HF or the dose the subject was on at the End of Study visit for the core study PANORAMA-HF prior to screening (Visit 500; refer to [Table 3-2](#)).

At Visit 501, subjects who meet eligibility criteria will start the study drug at dose level 1 or 2 ([Table 3-2](#)). Subjects who were on dose level 1 at the PANORAMA-HF End of Study (PANORAMA-HF visit 416) or who are on a low dose of ACEI/ARB (dose levels 1; [Table 3-3](#)) or not on an ACEI/ARB prior to screening (Visit 500) should start at dose level 1 at Visit 501.

[figure not shown]
Subjects who were on dose level 2, 3 or 4 at PANORAMA-HF visit 416 or who are on a higher dose of ACEI/ARB (dose levels 2, 3 or 4; [Table 3-3](#)) prior to screening (Visit 500) should start at dose level 2 at Visit 501 ([Table 3-2](#)) or at dose level 1 at investigator's discretion.

During the study, visits to assess safety will be conducted at Visit 501 and at 3-months intervals until the conclusion of the study (except for titration visits, which are at 2-week intervals). Unscheduled visits are allowed for subject's safety and for dose adjustment purposes

**Table 3-3 Total daily dose levels of commonly prescribed ACEI/ARBs for the purpose of comparing to dose levels of study drug**

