### **6.1.4 Treatment duration**

The study will continue up to 2 years from LPLV of part 2 of the core study (i.e., until approximately Dec-2023), receipt of local marketing authorization and commercial availability, or reaching maximum limit allowed by local regulations, whichever occurs first.

In countries where the sacubitril/valsartan is already authorized for pediatric use during the core study, patients may participate in the study for up to 1 year before being transitioned to commercially available product. If the formulation the patient is taking is not yet commercially available at the end of 1 year, the patient may continue in the study until the formulation becomes commercially available or until the maximum limit allowed by local regulations or until Dec-2023, whichever occurs first.

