Subjects should be seen for all visits/assessments as outlined in the assessment schedule or as close to the designated day/time as possible. If one visit is postponed or brought forward, it should not result in the next visit being postponed or brought forward. The next visit, if at all possible, should adhere to the original schedule in relation to Visit 501. Missed or rescheduled

visits should not lead to automatic discontinuation. Specific circumstances surrounding missed or rescheduled visits must be discussed with the study monitor. Subjects who prematurely discontinue the study for any reason should be scheduled for a final visit as soon as possible, at which time all of the assessments listed for the final visit (Visit 599) will be performed. At this final visit, all dispensed investigational product should be reconciled, and the adverse event and concomitant medications recorded on the eCRF.

As per [Section 4.6](#), during a Public Health emergency as declared by Local or Regional authorities i.e. pandemic, epidemic or natural disaster that limits or prevents on-site study visits, alternative methods of providing continuing care may be implemented by the investigator as the situation dictates. In case of missed visits/ assessments due to any such events/ disruptions, the site must refer to the “Panorama-HF OLE Patient visit guide during Public Health Emergencies” document and discuss with the site monitor for guidance on the steps that need to be followed for collection of missed data.

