 For child bearing potential females (CHBP) only. Urine pregnancy test is analyzed locally and done at all in-person scheduled/unscheduled visits on all female subjects  $\geq 11$  years of age and all female subjects who are  $<11$  years of age if they are menstruating. A serum pregnancy test is performed and analyzed at Visit 500 (if  $>14$  days after PANORAMA-HF EOS visit) and at Visit 599 respectively. Additionally, for all CHBP, a urine pregnancy test will be performed at monthly intervals during the study. The monthly urine pregnancy test can be performed either via: 1) monthly study site visits for urine pregnancy tests, or 2) providing the subject with urinary pregnancy tests for home monthly tests. See [Section 8.4.2](#) for additional details.

 Abbreviated laboratories consist of serum sodium, potassium, creatinine, eGFR (modified Schwartz formula).

Visit	500	501 **	502 *	503 *	504 *	505 *	50 6 †	507	508 †	509	510 †	511	512 †	513	514 †	515	516 †	517	518 520 522 †	519 521 523	U N S	599
Week/Month	Screening	Wk 0	Wk 2	Wk 4	Wk 6	Wk 8	Mo 3	Mo 6	Mo 9	Mo 12	Mo 15	Mo 18	Mo 21	Mo 24	Mo 27	Mo 30	Mo 33	Mo 36	Mo 39 Mo 45 Mo 51	Mo 42 Mo 48 Mo 54	EO S 	

 If Visit 500 is scheduled within 14 days of the PANORAMA-HF End of Study visit (Visit 416) and lab results from Visit 416 are available at Visit 500, the assessment results from PANORAMA-HF End of Study visit can be used for Visit 500 instead, except these discontinued study drug treatment early due to the implementation of the USM. Visit 501 is the visit for first drug administration. The inclusion/exclusion criteria and the abbreviated local lab at Visit 501 may be performed per the investigator's clinical judgement (e.g., if it is believed that the patient's health status may have changed since the screening visit) (See [Section 8.1](#) for details). Note: In addition to the scheduled complete and abbreviated laboratories per the Assessment Schedule, laboratory evaluations may also be performed at any scheduled or unscheduled visit based on the investigator's clinical judgement.

 Includes Prior and Concomitant Heart Failure Medications

 Complete labs at V521 and abbreviated labs at V519 and V523. If the EOS coincides with a scheduled visit, the assessments of EOS visit will take precedence.

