#### **8.4.3 Other safety evaluations**

Angioedema is a type of abrupt swelling that occurs under the skin and/or mucous membranes and is often localized to the head, neck, throat, and/or tongue, but may occur elsewhere, including the genitalia and intestines. Severe cases may be associated with airway compromise.

It is important that the investigator pays special attention to any swelling or edema that may resemble angioedema or angioedema-like events that may be reported by subjects. If such an event occurs, the investigator will complete angioedema case report forms to summarize the event, its treatment, and its ultimate outcome. This report along with the requisite medical documentation must be submitted to Novartis as soon as possible. Follow-up reports must be communicated to Novartis as soon as new information regarding the event becomes available. All hospital records related to the event must be communicated to Novartis.

The investigator may also be contacted by Novartis and be instructed to complete specific forms regarding AEs that may resemble an angioedema-like event. The investigator or his/her delegated staff must complete the required forms and provide the required medical records for all such events, regardless of whether the investigator views the event in question as angioedema or not.

All angioedema reports will be forwarded by Novartis to an external independent Angioedema Adjudication Committee for assessment. Information regarding this committee is outlined in [Section 10.2.3](#). Details on the procedures for reporting angioedema events will be provided to investigators in a manual.

[figure not shown]
The study duration will provide at least 1 year of growth and safety data in growing children, and this will be additional to the 1 year of data provided by the PANORAMA-HF study.

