2.1 Data analysis general information

Unless otherwise specified, the data will be analyzed according to the study protocol using SAS 9.4 or higher and R 3.4.3 or higher, by Novartis personnel.

In general, continuous variables will be summarized using number of observations, mean, standard deviation, median, quartiles, minimum and maximum. Categorical variables will be summarized using frequencies and percentages. Unless otherwise specified, the by age group summaries will include: summary for the two age groups (6 years and older, 1 year to < 6 years) and summary for the entire analysis set.

Study completion is defined as having reached the end of study visit (December 2023 from Protocol Amendment V.01 and later versions or December 2022 for Protocol V.00) while on treatment, or having completed 12 months of study while being on treatment and being transitioned to commercial Entresto.

Data from all study centers will be combined.

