2.8.4.3 Changes in height, weight and head circumference

Summary statistics and change from baseline will be provided for weight, height, and head circumference (patients ≤ 3 years) by visit and age group (and overall). Subgroup analysis of height (i.e., height, z-score for height and age-adjusted percentile for height) will be performed for patients satisfying the criterion of being within the age range of 2-9 years at each 12-month visit throughout the OLE study and for overall group. Summary statistics by yearly visit will be provided.

In addition, age-adjusted percentile will be calculated for height, weight and BMI; Z-score will be calculated for height, as done by the WHO to assess child growth. For more details, see [World Health Organization \(WHO\) 1997](#).

The same summaries as for the raw values will be produced for these Z-scores. In addition, shift tables will be produced using the following rules for severe low/moderate low/normal classification ([Dibley et al, Mei Z and Grummer-Strawn LM, World Food Programme](#)):

- Z-score < -3: severe low
- -3 ≤ Z-score < -2: moderate low
- Z-score ≥ -2: normal

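### The stated 1-year minimum of growth data does not follow from the exit rules, and a child who completes at Month 12 may have no required post-baseline height in the database

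*Protocol*

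**What the plan says.** **Duration.** Protocol 8.4.3 says: "The study duration will provide at least 1 year of growth and safety data in growing children". Protocol Section 3 gives a matching range: "the duration of the study varies from 1 to approximately 4.5 years". The exit rules are in 4.2 and 6.1.4. Where paediatric use was authorised during the core study, "patients may participate in the study for up to 1 year before being transitioned to commercially available product"; a child may stay longer only if the formulation in use is not yet on the market. In general the study runs to about December 2023, or ends earlier on "receipt of local marketing authorization and commercial availability, or reaching maximum limit allowed by local regulations, whichever occurs first".

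**Completion.** SAP 2.1 counts as study completion either reaching the end-of-study visit on treatment or "having completed 12 months of study while being on treatment and being transitioned to commercial Entresto".

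**Final visit.** Footnote 6 of Table 8-1 says: "If the EOS coincides with a scheduled visit, the assessments of EOS visit will take precedence". For premature leavers, protocol Section 8 says that "all of the assessments listed for the final visit (Visit 599) will be performed".

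**Height analysis.** SAP 2.8.4.3 plans change from baseline in height, height z-scores, age-adjusted percentiles and z-score shift tables. It also plans a subgroup of children aged 2 to 9 years at each 12-month visit, with the statement "Summary statistics by yearly visit will be provided".

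**The concern.** There are two linked problems.

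First, the protocol presents 1 year of growth data as a floor, while its participation rules make 1 year a ceiling for some children and set no floor for others.

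Second, the assessment schedule may not capture even the 12-month height of a child who leaves at 12 months exactly as planned. Visit 509 (Month 12) is the first post-baseline visit at which height goes into the database. If that visit becomes the end-of-study visit, and the end-of-study visit has no height, the child contributes a baseline height and nothing else to the SAP's growth analysis.

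Growth is a named safety output of this extension. Children who move to commercial product at 12 months come from countries where the drug was already authorised. If their Month 12 height is missing, the Month 12 column mainly describes children who stayed longer. Children who leave between yearly visits also lose the last part of their growth on drug from the database.

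**Working it through.** **1. Stated range of duration.**
- Upper end: first patient first visit on 02-May-2019 (Amendment 1 rationale) to December 2023 is 4.58 years (to 1 December) to 4.67 years (to 31 December). The last scheduled visit, Month 54, gives 54/12 = 4.5 years. The figure of about 4.5 years is reproduced.
- Lower end: the exit rules give at most 12 months in already-authorised countries (formulation exception aside) and no lower bound elsewhere. A minimum of 1 year per child is not reproduced.

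**2. Height marks in Table 8-1.** Columns are shifted in the text form of the table: read literally, six of the seven follow-up height marks fall on telephone visits. I therefore matched the sequence of marks to the in-person visits.
- Height: `x` at Visits 500 and 501, then seven marks, `s x s x s x s`. There are seven in-person follow-up columns before the unscheduled and final visits: 507, 509, 511, 513, 515, 517 and 519/521/523. The match puts database heights (`x`) at Months 12, 24 and 36 and source-only heights (`s`) at Months 6, 18 and 30. No mark is left for Visit 599, and the last two cells are blank.
- Weight: three marks follow Visit 517, enough for 519/521/523, unscheduled and 599.
- Head circumference: five marks follow Visit 501, enough for 509, 513, 517, 519/521/523 and 599.
- If the last height mark did belong to Visit 599, it is `s`, so still source-only.

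**3. Post-baseline heights by time of exit**, with Visit 599 replacing a coinciding scheduled visit:

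| Exit | In database | Source only |
|---|---|---|
| Up to and including Month 6 | 0 | 0 |
| After Month 6, up to and including Month 12 | 0 | 1 (Month 6) |
| After a separate Visit 509, up to and including Month 18 | 1 (Month 12) | 1 (Month 6) |

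With a database height at Visit 599, a Month 12 leaver would have 1 instead of 0.

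**4. A late starter.** Two years before December 2023 puts the core study's last visit at about December 2021. With the 30-day window, the latest start is about January 2022. Exit in December 2023 gives about 23 months on study, so Visit 513 (Month 24) is not reached.
- Last database height at Month 12: 23 − 12 = 11 months not captured in the database (11/23 = 48%).
- Last source height at Month 18: 23 − 18 = 5 months with no height of any kind (5/23 = 22%).

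**5. Recovery in the SAP.** I found no rule that assigns Visit 599 results to the scheduled visit they replace. SAP 2.8.3 fills missing laboratory values from unscheduled visits only, and SAP 2.8.4.3 has no comparable rule for height or weight.

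**The case against.** The strongest objection is that the empty Visit 599 height cell is read from a damaged table. Taken literally, the weight and head-circumference rows are blank at 599 too. The seven-mark match also puts a single source-only mark on 519/521/523, which makes Month 48 source-only and breaks the yearly pattern. This stands as a reason to check the printed table. It does not remove the point, because neither reading yields a database height at Visit 599.

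Several stronger conclusions might be inferred, and the documents do not support them:
- *That a Month 12 completer has no post-baseline height at all, or that 48% of the late starter's growth is unmeasured.* Six-monthly source heights exist. The loss is from the database.
- *That footnote 6 cancels the Visit 509 height.* Precedence does not forbid taking it as well. The text simply does not require it.
- *That 8.4.3 promises each child a year.* The sentence is about what the study's duration provides, and SAP 2.1 shows that 12 months was the planned stay before transition. By 31 July 2021, 173 patients were enrolled, and follow-up could run to about December 2023, so many could pass 1 year. The wording still conflicts with a rule that has no minimum stay.
- *That the SAP pools all exits in one end-of-study column.* It does not say so. What can be said is that it gives no rule for placing Visit 599 values.

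**Conclusion.** The point holds in a limited form. The duration statements in 8.4.3 and Section 3 do not follow, as a per-child minimum, from 4.2 and 6.1.4, and these passages must be reconciled. As far as Table 8-1 can be read, no database height is listed at Visit 599. A child who completes at Month 12 under SAP 2.1 may therefore finish with no required post-baseline height in the database and only a Month 6 height in source. For the latest starters, about 11 of 23 months of growth would be outside the database, about 5 of them with no height at all.

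This rests on the reading of the table in step 2, on end of study coinciding with Month 12, and on a site doing no more than the final visit lists. The documents do not say how many children this affects. It concerns early and 1-year leavers and the last stretch of follow-up in others, not the whole cohort. It should be corrected because growth is a stated safety output and the correction is small.

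**What to change.** 1. Check the printed Table 8-1. If the Visit 599 height cell is empty or source-only, make it a height entered in the eCRF.
2. State in the SAP that Visit 599 height, weight, vital signs and laboratory values are assigned to the scheduled visit they replace, or otherwise to the nearest one by study day. Keep a separate last-value row.
3. Reconcile 8.4.3 and Section 3 with 4.2 and 6.1.4. Report the number of children with a Month 12 height in place of the assertion of a 1-year minimum.

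The cost is one quick measurement at an existing visit where weight already appears to be taken, a short SAP rule, and a slightly less favourable claim. If visits are already complete, the SAP rule, the count and the rewording still apply, and a height recorded in source near the exit date could be entered.

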#### **8.4.4 Appropriateness of safety measurements**

The safety and clinical laboratory assessments performed in this study are similar to those used in the core study PANORAMA-HF (CLCZ696B2319). These assessments are appropriate for an investigational drug with the mechanism(s) of action of sacubitril/valsartan (angiotensin receptor neprilysin inhibitor), the safety profile described in the sacubitril/valsartan Investigator Brochure, and the indication/subject population under study.

### **8.5 Additional assessments**

No additional tests will be performed on subjects entered into this study.

## **9        Study discontinuation and completion**

### **9.1      Discontinuation**

#### **9.1.1    Discontinuation of study treatment**

Discontinuation of study treatment for a subject occurs when study treatment is stopped earlier than the protocol planned duration, and can be initiated by either the subject or the investigator. In this study, if the study treatment is permanently discontinued, the subject should be discontinued from the study and EOS visit (Visit 599) should be conducted ([Section 6.5.1](#)).

The investigator must discontinue study treatment for a given subject if, he/she believes that continuation would negatively impact the subject's well-being.

Study treatment must be discontinued under the following circumstances:

- Subject/guardian decision
- Pregnancy
- Use of prohibited treatment as per recommendations in the prohibited treatment section
- Any situation in which study participation might result in a safety risk to the subject
- Any laboratory abnormalities that in the judgment of the investigator prevents the subject from continuing participation in the study
- A consecutive 3-month interruption of study treatment

If discontinuation of study treatment occurs, the investigator should make a reasonable effort to understand the primary reason for the subject's premature discontinuation of study treatment and record this information.

Subjects who discontinue study treatment or who decide they do not wish to participate in the study further should NOT be considered withdrawn from the study UNLESS they withdraw their consent (see withdraw of informed consent section,).

The investigator must also contact the IRT to register the subject's discontinuation from study treatment.

#### **9.1.2    Withdrawal of informed consent**

Subjects may voluntarily withdraw consent to participate in the study for any reason at any time. Withdrawal of consent occurs only when a subject:

- Does not want to participate in the study anymore, and
- Does not allow further collection of personal data

In this situation, the investigator should make a reasonable effort (e.g. telephone, e-mail, letter) to understand the primary reason for the subject's decision to withdraw his/her consent and record this information.

Study treatment must be discontinued and no further assessments conducted, and the data that would have been collected at subsequent visits will be considered missing.

Further attempts to contact the subject are not allowed unless safety findings require communicating or follow-up.

All efforts should be made to complete the assessments prior to study withdrawal. A final evaluation at the time of the subject's study withdrawal should be made as detailed in the assessment table.

Novartis will continue to keep and use collected study information (including any data resulting from the analysis of a subject's samples until the time of withdrawal) according to applicable law.

For the United States (US) and Japan: All biological samples not yet analyzed at the time of withdrawal may still be used for further testing/analysis in accordance with the terms of this protocol and of the informed consent form.

For European Union (EU) and Rest of World (RoW): All biological samples not yet analyzed at the time of withdrawal will no longer be used, unless permitted by applicable law. They will be stored according to applicable legal requirements.

#### **9.1.3 Lost to follow-up**

For subjects whose status is unclear because they fail to appear for study visits without stating an intention to discontinue or withdraw, the investigator must show "due diligence" by documenting in the source documents steps taken to contact the subject, e.g. dates of telephone calls, registered letters, etc. A subject should not be considered as lost to follow-up until due diligence has been completed or until the end of the study.

[figure not shown]
